5.1 Outcome definitions

5.1.1 Primary clinical outcome

The primary clinical outcome is a composite of death and organ support by 30 days. Patients who have died on or before day 30 post randomisation are assigned the worst possible score of 31, and surviving patients are scored by the number of calendar days on which any type of organ support was given, starting from day 1 (the day on which the patient was randomised) up to and including day 30. Any organ support during the first 30 days will be included, regardless of whether the support was during the index PICU admission, on a ward, or during a re-admission to PICU.

5.1.2 Primary health economic outcomes - Incremental costs, quality-adjusted life years (QALYs) and net monetary benefit at 12 months

Economic costs will be calculated from patient-level resource use data captured through trial case report forms linked to PICANet, Hospital Episode Statistics, and follow-up patient questionnaire. Resource use for delivering the interventions, length of stay in PICU/HDU and acute hospital, for the index admission and any readmission before 12 months, and from use of personal health services after acute hospital discharge within 12 months post-randomisation will be measured. Appropriate unit costs data will be obtained from the NHS Payment by Results database, unit costs of health and social care (PSSRU) and from local Trust Finance Departments.

The health outcome for the economic evaluation will be summarised using QALYs, which unites quantity (survival) and quality of life into a single metric. To do this, HRQoL, which is measured on an index scale of 1 (equals full health) and 0 (equals death), at 12 months will be assessed using the Paediatric Quality of Life Generic Core Scales (PedsQL) and CHU-9D instruments. HRQoL data will be collected via age-appropriate Paediatric Quality of Life Generic Core Scales (PedsQL) and CHU-9D instruments. The responses to PedsQL questionnaire from eligible surviving children at 12 months will be mapped onto the Child Health Utility 9D (CHU-9D) score (Lambe et al, 2018). The responses to CHU-9D questionnaire will be converted into utility score using recommended algorithm (Stevens, 2012). QALYs will be calculated by valuing each patient's survival time by their HRQoL at 12 months according to the "area under the curve" approach. For 12-month survivors, QALYs will be calculated using the HRQoL scores at 12 months, assuming HRQoL of zero at randomisation, and a linear interpolation between randomisation and 12 months. For decedents between randomisation and 12 months, we will assume zero QALYs.

5.1.3 Secondary outcomes

5.1.3.1 Incremental costs at 30 days

Costs at 30 days will be calculated from patient-level resource use data, length of stay in PICU/HDU and acute hospital, for the index admission and any readmission before 30 days.

5.1.3.2 Mortality at PICU discharge, 30 days, 90 days and 12 months

Mortality at discharge from the critical care unit will be defined as death due to any cause before discharge to any location providing a level of care less than Level 2 (high dependency care).

5.1.3.3 Time to liberation from ventilation

Liberation from ventilation is defined as the start of a continuous period of at least 48 hours free from ventilation. The time to liberation from ventilation will be measured from randomisation to the start of the first such period.

5.1.3.4 Duration of organ support.

Duration of organ support is defined as for the primary clinical endpoint (number of calendar days from day 1 to 30 on which any support was given).

5.1.3.5 Length of PICU and acute hospital stay

Length of PICU stay will be measured in hours from randomisation to discharge, plus the duration from admission to discharge of any subsequent re-admissions to a PICU starting up to and including day 30.

5.1.3.6 Functional status at PICU discharge

Functional status at PICU discharge will be measured in surviving patients at the time of first discharge from PICU following randomisation, using the Paediatric Cerebral Performance Category (PCPC) and Paediatric Overall Performance Category (POPC) scales, which categorise performance on a 5 point scale from best (1) to worst (5).

5.1.3.7 Health related quality of life at 12 months

Health-related quality of life at 12 months will be measured using the Paediatric Quality of Life Inventory (Peds-QL)32 and the Child Health Utility 9D (CHU-9D), completed by parents at twelve months post-randomisation.

The PEDS-QL instrument uses a different set of question of each age group of 1-12 months; 13-24 months; 2-4 years; 5-7 years; 8-12 years; 13+years. For each age group an overall score is calculated on a scale of 0-100 with higher scores indicating better quality of life. In infants under 2 years five subscales are defined, relating to physical functioning, physical symptoms, emotional functioning, social functioning, and cognitive functioning, and in children of 2 years and over four subscales are defined, relating to physical functional functioning, social functioning and school functioning.

CHU-9D was developed with children aged 7-17 and is designed to produce utility values for use in calculating quality adjusted life years (QALYs)

5.2 Clinical effectiveness analysis methods

5.2.1 Primary outcome

The primary clinical outcome will be compared between arms using a Wilcoxon rank-sum test with two-sided p-value of 0.05. The primary effect estimate will be the probabilistic index (the probability that the intervention is superior to the control for either mortality and/or duration of organ support), which will be presented with a 95% confidence interval.

Ordered logistic regression will be used firstly in a sensitivity analysis to estimate the unadjusted proportional odds ratio, and secondly to estimate the proportional odds after adjusting for the following baseline variables:

- age (<12 months / ≥12 months);
- primary reason for admission (lower respiratory tract infection vs. Other);
- severity of abnormality of gas exchange: SF ratio <221 with PEEP ≥5 vs. Other
- predicted mortality at PICU admission (measured using the PIMS 3⁴ score)
- site (as a random effect)

Subgroup analyses will be performed to test for interactions between the effect of allocated treatment group and the following baseline covariates:

- age (<12 months / ≥12 months);
- Age adjusted heart rate centile
- Haemoglobin level at admission

The interaction effect for continuous covariates (haemoglobin at admission) will be illustrated by calculating the adjusted hazard ratio within five categories at quintiles of the continuous variable. Heart rate will be corrected for age by grouping into centile bands⁵.

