2.2 Randomisation

Patients will be randomised on a 1:1 basis to either a liberal (>94%) or conservative (88-92%) SpO2 target, using minimisation to balance the arms with respect to age (<12 months / \geq 12 months); site; primary reason for admission (lower respiratory tract infection vs. Other); and severity of abnormality of gas exchange: SF ratio <221 with PEEP \geq 5 vs. Other.

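### The primary Wilcoxon test and probabilistic index ignore all four minimisation factors, so the p-value is too large and the interval too wide to the extent that those factors are prognostic

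*SAP*

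**What the plan says.** On allocation, SAP 2.2 states: "Patients will be randomised on a 1:1 basis to either a liberal (>94%) or conservative (88-92%) SpO2 target, using minimisation to balance the arms". The factors are age (below 12 months or not), site, primary reason for admission (lower respiratory tract infection or other) and severity of gas-exchange abnormality.

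On the deciding analysis, SAP 5.2.1 states: "The primary clinical outcome will be compared between arms using a Wilcoxon rank-sum test with two-sided p-value of 0.05". It continues: "The primary effect estimate will be the probabilistic index", with a 95% confidence interval. No stratum or covariate is attached to either.

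Adjustment comes in the next paragraph of 5.2.1: "Ordered logistic regression will be used firstly in a sensitivity analysis to estimate the unadjusted proportional odds ratio, and secondly to estimate the proportional odds". The second of these models is the adjusted one. Its covariates are all four minimisation factors (site as a random effect) plus the PIM 3 predicted mortality. This model supports the primary analysis and does not decide the trial.

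SAP 2.3 bases 90% power on rank-based methods, by simulation from pilot data, and mentions no adjustment. The SAP gives no reason for leaving the primary analysis unadjusted.

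**The concern.** Minimisation forces the arms to agree closely on the four factors, so any outcome variation due to them is largely removed from the difference between arms. The variance in a two-sample rank-sum test is the one that applies under simple randomisation, and it still counts that variation. If the factors are prognostic, the standard error is too large. The test then rejects less often than 5% under the null, and the interval for the probabilistic index is wider than it need be.

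What is at stake is efficiency in the result that decides the trial. If the Wilcoxon test and the adjusted model fall on opposite sides of 0.05, the SAP lets the less efficient one decide. No adjusted version of the probabilistic index is planned, so the supporting model cannot be set beside the headline estimate on the same scale.

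**Working it through.** **The plan's own figure.** The 10% allowance in 2.3 is consistent with 1836 evaluable patients: 1836 / (1 − 0.10) = 2040. The 1836 itself cannot be reproduced, because the pilot distribution of organ-support duration is not in the SAP. The sample size is therefore neither confirmed nor refuted here, and the planned 90% power is taken as given.

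**Inputs.** From the SAP: two-sided alpha 0.05 (5.2.1), so z = 1.96; power 90% (2.3), so z = 1.2816; sum 3.2416. Assumed: R², the share of outcome-rank variance explained by the balanced factors, over a range of 0 to 20%. The SAP gives no value.

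**Formulas.** With good balance, the variance of the unadjusted statistic is (1 − R²) times what the test assumes. Then:

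- true type I error = 2 × [1 − Φ(1.96 / √(1 − R²))]
- overstatement of the standard error = 1 / √(1 − R²) − 1
- power of the planned test = Φ(1.2816 / √(1 − R²))
- power with adjustment = Φ(3.2416 / √(1 − R²) − 1.96)
- sample-size multiple k at which the planned test matches the adjusted one, from (3.2416√k − 1.96) / √(1 − R²) = 3.2416 / √(1 − R²) − 1.96. This gives √k = 1 + 1.96 × (1 − √(1 − R²)) / 3.2416.

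For R² = 10%, √0.90 = 0.9487. Type I error is 2 × [1 − Φ(2.066)] = 0.039. Planned-test power is Φ(1.351) = 0.912, and adjusted power is Φ(3.417 − 1.96) = Φ(1.457) = 0.927. √k = 1 + 1.96 × 0.0513 / 3.2416 = 1.031, so k = 1.063.

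| R² (assumed) | True type I error | SE overstated by | Power, planned test | Power, adjusted | Extra patients to match |
|---|---|---|---|---|---|
| 0 | 5.0% | 0 | 90.0% | 90.0% | 0 |
| 5% | 4.4% | 2.6% | 90.6% | 91.4% | 3.1% |
| 10% | 3.9% | 5.4% | 91.2% | 92.7% | 6.3% |
| 20% | 2.8% | 11.8% | 92.4% | 95.2% | 13.2% |

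On 2040 patients the last column is 2040 × 0.031 ≈ 63, 2040 × 0.063 ≈ 129 and 2040 × 0.132 ≈ 269.

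**Simulation check.** Minimisation was simulated with 1836 patients, 15 sites, three binary factors and a biased coin of 0.8 (all but the 1836 assumed). The plain Wilcoxon test was compared with a rank regression on the four factors. The effect was about a 10% shorter duration. Monte Carlo standard error is about 0.006 under the null and 0.02 under the effect.

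| R² | Null rejection, plain | Null rejection, adjusted | Power, plain | Power, adjusted |
|---|---|---|---|---|
| about 1% (factors not prognostic) | 0.048 | 0.045 | 0.81 | 0.81 |
| about 5% | 0.045 | 0.048 | 0.78 | 0.81 |
| about 14% | 0.033 | 0.048 | 0.76 | 0.82 |
| about 27% | 0.022 | 0.053 | 0.67 | 0.81 |

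The direction matches the formulas. Adjustment costs nothing visible when the factors are irrelevant. The loss is small at 5% and material from about 15%.

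**Interim look.** SAP 2.6 sets p<0.001 without naming a test. If the plain Wilcoxon test is used, the true level is 2 × [1 − Φ(3.2905 / √(1 − R²))], or about 0.0007, 0.0005 and 0.0002 for R² of 5%, 10% and 20%.

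**The case against.** The strongest defence is that a simple test with few assumptions, backed by a pre-specified adjusted model containing every minimisation factor, is a legitimate choice. Any error is on the safe side, and the sample size was set for rank-based methods with no adjustment mentioned, so design and analysis agree. All of this stands. It limits the size of the point but does not remove it: the supporting model does not decide the trial and reports an odds ratio, not the probabilistic index.

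A reader might infer three stronger things that the SAP does not support.

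- *That the trial falls short of 90% power.* By the formulas above, the planned test stays at or above 90%. The fall from 0.81 to 0.67 in the simulation arises because stronger factors add outcome variation in an assumed data model. Only the gap between the two tests is informative there.
- *That the gain is worth 5%, 11% or 25% more patients.* That is 1 / (1 − R²) − 1, which compares adjustment with an unadjusted test under simple randomisation. Against the planned test under forced balance, the figures are 3%, 6% and 13%.
- *That the p-value is certainly too large, because the factors were chosen for predicting outcome.* SAP 2.2 says only that they are balanced. At R² = 0 there is no effect, and at 2% type I error is still 4.8%.

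**Conclusion.** The point holds in conditional form. The primary test and estimate use none of the four minimisation factors, and to the extent that these predict outcome, the p-value is too large and the interval too wide. For R² of 5% to 20%, type I error is about 4.4% to 2.8% instead of 5%, and 0.8 to 2.8 percentage points of power are forgone (91.4 − 90.6 and 95.2 − 92.4). These figures rest on an assumed R², on close balance from the minimisation, and on the planned 90% being correct for the unadjusted test.

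This is a missed improvement, not a validity error. Type I error is not inflated and no planned operating characteristic is shown to fail. Nor is the information wholly thrown away, since the adjusted ordinal model in 5.2.1 uses it outside the deciding analysis. The change is worth making because it needs no new data.

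**What to change.** In SAP 5.2.1, make the primary test and probabilistic index account for age group, reason for admission, severity of gas exchange and site. Either of these would do:

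- a probabilistic index model, or another covariate-adjusted rank analysis, with the four factors; or
- the adjusted ordinal model already specified, made primary. This changes the headline measure to an odds ratio and relies on proportional odds, which 5.2.3 already allows may not hold.

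A stratified Wilcoxon (van Elteren) test over the eight cells of age, reason and severity would be only a partial answer, because it omits site.

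State whether the index is marginal (over all between-arm pairs, as the plain Wilcoxon test implies) or conditional on the factors. Keep the plain Wilcoxon test as a sensitivity analysis, and name the same primary test for the interim look in 2.6. If the sponsor prefers the unadjusted analysis, 5.2.1 should at least give the reason.

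The cost is SAP wording and a modest amount of code, settled before outcome data are seen. The downside is a slightly more complex headline method and, with a conditional index, a slightly different estimand.

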2.8 Timing of outcome assessments

Following randomisation, observations are recorded hourly on the hour (+/-15 minutes) for 7 days (or until PICU discharge if earlier) and include receipt of invasive ventilation (yes/no) and, where children are on invasive ventilation, SpO2, mean airway pressure (MAP), and FiO2. For days 8 onwards (or until PICU discharge if earlier), the same observations are recorded twice daily at 09:00 and 21:00 (+/- 1 hour).

Receipt of any other type of organ support (yes/no) is recorded once daily until day 30 or PICU discharge.

Other outcomes are collected at discharge from critical care (date/time of liberation from ventilation, survival status at PICU discharge and discharge method, and functional status as measured using the Paediatric Cerebral Performance Category (PCPC) and Paediatric Overall

performance Category (POPC)), and at ultimate discharge from acute hospital (survival status at hospital and ultimate PICU discharge, locations of care after PICU discharge).

Specified adverse events and serious adverse events are collected from randomisation until 30 days after randomisation or discharge from PICU, whichever is later.

Long term survival is collected at 12 months, using either linkage to national survival data (NHS Digital) or by local research teams. Once 12 month survival status is known, PEDS-QL and CHU-9D quality of life questionnaire will be emailed or posted to consenting parents/legal guardians.

3 Statistical Principles

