4.2 Eligibility

4.2.1 Inclusion Criteria

- Less than 16 years and more than 38 weeks corrected gestational age
- Enrolled within six hours of first meeting all the following criteria;
 - Accepted to a participating PICU as an unplanned admission

- Receiving invasive mechanical ventilation with supplemental oxygen for abnormal gas exchange

- Face-to-face contact with PICU staff or transport team

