4.6 Baseline patient characteristics

Baseline data is collected at critical care admission via data linkage to PICANET, and directly via trial CRF for physiology at randomisation. The following baseline demographic and clinical data will be summarised in the ITT population, by allocated treatment group, (using mean, standard deviation,

median and interquartile range (IQR), or counts and percentages for binary and categorical variables), but not subjected to statistical testing:

Age (years) – median and IQR, and number and % by age group (<=12 months, >12 months))

Ethnic group

Sex (male, female) – number and %

Arterial PaO2, base excess, lactate, systolic blood pressure, and mean airway pressure at randomisation – median and IQR, mean and SD

Comorbidities - number and % by type of comorbidities (as specified on the CRF)

Main reason for PICU admission (from PICANET linkage)

5 Analysis

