5.2.2 Secondary outcomes

Mortality at discharge from critical care and at 30 days will be compared between groups using Fisher's exact test. If the number of events allows, logistic regression will be used to compare mortality between groups adjusted for baseline variables.

Mortality at 90 days and at 12 months will be estimated by arm, using Kaplan-Meier methods with patients censored at last available follow-up. If the number of events allows, Cox regression will be used to compare mortality between groups adjusted for baseline variables.

Time to liberation from ventilation will be reported as median time (with 95% confidence interval) by arm, calculated using Kaplan-Meier methods. Unadjusted and adjusted hazard ratios will be calculated using Cox regression. Patients who die on ventilation will be censored at date & time of death.

Duration of organ support to day 30 (calculated as for the primary clinical endpoint) will be compared between groups using a Wilcoxon rank-sum test, in patients stratified by survival status. Duration of organ support by type of support (respiratory invasive; respiratory non-invasive; cardiovascular; renal; other) will be reported by group using medians and interquartile ranges, and counts and percentages of patients ever receiving, but not formally tested for differences between groups. Length of PICU and acute hospital stay will be compared between groups using a Wilcoxon rank-sum test, and reported by group using medians and interquartile ranges, in patients stratified by survival status.

Functional status at PICU discharge will be reported as counts and percentages in each of five possible categories.

All adjusted analysis will include the baseline variables previously listed in section 5.2.1.

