use multilevel models (MLM) to handle clustering and avoid potential biases and incorrect inferences. The CEA will adjust for same baseline covariates as for the analysis of primary clinical outcome to adjust for baseline imbalances between the randomised arms The incremental results from multiply-imputed datasets will summarised using Rubin's rule {Rubin, 1987 #54}.

The CEA will report the mean (95% confidence interval) incremental costs, QALYs and net monetary benefit at 12 months. Incremental costs at 30 days will also be reported. The incremental net monetary benefit (INB) of the intervention compared to control at 12 months will be calculated by multiplying the mean gain or loss in QALYs by a recommended thresholds in the UK (£20,000) and subtracting the incremental cost. The probability that the intervention is cost-effective compared to control will be presented at different levels of WTP for a QALY gain.

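### Age enters every adjusted analysis only as under or over 12 months although age in years is held: a valid choice, with a small and avoidable loss of efficiency

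*SAP*

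**What the plan says.** Section 5.2.1 lists the covariates for the adjusted ordered logistic model. Age appears as "age (<12 months / ≥12 months" and gas exchange as "severity of abnormality of gas exchange: SF ratio <221 with PEEP" of at least 5 against the rest. Both cuts are those used for minimisation in section 2.2. The list also holds admission reason, PIM 3 predicted mortality (no categories stated) and site as a random effect.

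The list is then reused. Section 5.2.2: "All adjusted analysis will include the baseline variables previously listed in section 5.2.1". Section 5.3: "The CEA will adjust for same baseline covariates as for the analysis of primary clinical outcome". Section 5.4 builds the imputation model for missing baseline variables from the same covariates.

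Eligibility in section 4.2.1 is "Less than 16 years and more than 38 weeks corrected gestational age", and section 4.6 will report "Age (years) – median and IQR". The primary test in 5.2.1 is an unadjusted Wilcoxon rank-sum test, with the probabilistic index as effect estimate.

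**The concern.** A child of 13 months and one of 15 years carry the same age value in every adjusted model. Any prognostic gradient above 12 months is left in the residual, or in the unmodelled part of a non-linear model, although the number that would capture it is already held.

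This reaches further than one sensitivity model. Section 1.2.1 lists incremental costs, QALYs and net monetary benefit at 12 months as a primary objective. Section 5.3 analyses them with covariate adjustment and specifies no unadjusted version, so for that objective the coarse list is the main analysis. Age could well matter there. A survivor's QALYs rest on quality of life at 12 months (5.1.2). A child aged at least 12 months at randomisation is at least 2 years old by then, and so falls under one of four PedsQL age versions (2-4, 5-7, 8-12 and 13+ years; 5.1.3.7). That makes an age gradient plausible; it does not show its size.

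**Working it through.** **1. The plan's own figure.** Section 2.3 gives 2040 children with 10% loss: 2040 × 0.9 = 1836, or 918 per arm. It came from simulation on pilot data that are not shown, so it cannot be reproduced. The normal formula n = 2·SD²·(1.960 + 1.282)²/12² returns 918 per arm only at an SD of about 79.3 hours. A Wilcoxon simulation (assumed lognormal hours, calendar days capped at 30, 7.5% deaths ranked worst) gave 92% power at a coefficient of variation of 0.60 and 87% at 0.66, so 90% is plausible. The figure serves below only as a benchmark. The primary test is unadjusted, so this point does not alter it.

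**2. What a cut keeps.** Let k be the squared correlation between a covariate and its two-level version. With an assumed 40-60% of infants and a declining age distribution up to 16 years, the 12-month cut keeps k = 0.41-0.51 of a linear age effect and 0.71-0.72 of a log-age effect. For a normal covariate with 50-80% of children below the cut, k = 0.64-0.49.

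**3. Linear model (cost-effectiveness, taking the seemingly unrelated regression as linear).** If the continuous terms explain a share R² of variance and the binary ones k·R², the ratio of standard errors, continuous to binary, is √[(1 − R²)/(1 − k·R²)]. The SAP gives no prognostic strength, so R² is assumed. Reduction in standard error:

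| R² | k = 0.41 | k = 0.55 | k = 0.72 |
|---|---|---|---|
| 5% | 1.5% | 1.2% | 0.7% |
| 10% | 3.1% | 2.4% | 1.5% |
| 15% | 4.8% | 3.7% | 2.4% |

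Example: R² = 10%, k = 0.55 gives √(0.900/0.945) = 0.976. R² here means variance beyond what PIM 3, admission reason and site already explain. If only age can be made continuous, read the table at the R² of age alone.

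**4. Same idea on the power scale.** From a notional 90% unadjusted base, power = Φ(3.242/√(1 − k·R²) − 1.960), with k = 1 for continuous terms. The equivalent number of children is 1836 × [1 − (1 − R²)/(1 − k·R²)]. For k from 0.36 to 0.75:

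| R² | Loss, power points | Children |
|---|---|---|
| 1% | 0.1-0.2 | 5-12 |
| 5% | 0.4-0.9 | 24-60 |
| 10% | 0.7-1.7 | 50-122 |
| 15% | 1.0-2.5 | 78-186 |

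The SAP sets no power for any adjusted model, so these are scale markers only.

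**5. Ordered logistic model.** Simulation with 1836 children, true log odds ratio −0.27, two assumed normal covariates, and the three models fitted to the same 60 data sets per setting. Entries are mean estimate / SE / absolute z:

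| Latent R² | Unadjusted | Binary | Continuous |
|---|---|---|---|
| 5% | −0.263 / 0.082 / 3.22 | −0.268 / 0.082 / 3.27 | −0.273 / 0.082 / 3.32 |
| 18% | −0.213 / 0.082 / 2.61 | −0.240 / 0.082 / 2.92 | −0.262 / 0.082 / 3.18 |

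The standard error does not move. With binary terms the estimate is pulled towards the null, and z falls with it.

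**6. Logistic and Cox models.** In a similar simulation, adding continuous to binary terms took the logistic standard error (about 7% mortality) from 0.1993 to 0.1997 with weaker covariates and from 0.1995 to 0.2002 with stronger ones. Mean z was 1.50 v 1.50 and 1.58 v 1.59. The Cox standard error stayed at 0.0488. No interval narrows.

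**7. Which values are in hand.** Age in years: yes, section 4.6. SF ratio: not shown. Section 4.6 collects data "directly via trial CRF for physiology at randomisation", but the items it names are PaO2, base excess, lactate, systolic blood pressure and mean airway pressure, not SpO2, FiO2, SF ratio or PEEP. The hourly records of section 2.8 ("where children are on invasive ventilation, SpO2, mean airway pressure (MAP), and FiO2") begin after randomisation and cannot serve as baseline covariates.

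**The case against.** The strongest reply is that this is a modelling preference. Adjusting for minimisation factors in the form used to allocate is conventional and coherent. The primary result does not depend on it. PIM 3 already carries severity information, and any overlap shrinks the gain. Extra terms also have a price in the mortality models, which section 5.2.2 plans only if events allow. All of that stands, and it limits the size of the point. It does not show that adding continuous age would be wrong or costly.

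A reader might also infer more than the SAP supports:

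- *That all adjusted intervals are too wide.* This is true only of a linear model; steps 5 and 6 show that odds- and hazard-ratio standard errors do not fall.
- *That the numeric SF ratio is held, like age.* Applying the minimisation cut shows that a category was assigned, not that the number was stored. The factor is also a joint SF and PEEP criterion, which a continuous SF ratio alone does not represent.
- *That chance imbalance within a category biases the result.* Randomisation-based inference already allows for it.

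**Conclusion.** The point holds as a minor inefficiency. The covariate list is valid, but it leaves unused a baseline value that is already collected, in every adjusted clinical model and in the analysis of a primary health economic objective.

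The clearest loss is in the cost-effectiveness model: about 1-4% in standard error at k = 0.55, and 0.7-4.8% over the range of k tried for age, if age and severity together explain 5-15% of variance. It is smaller if PIM 3 overlaps or if only age can be made continuous. In the ordinal model the loss is slight attenuation and some power; in the logistic and Cox models it is close to nil on the simulations above. Every size rests on assumed prognostic strength and an assumed age mix.

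The primary Wilcoxon test, the probabilistic index and the sample size are unaffected.

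**What to change.** In section 5.2.1 keep the minimisation factors as they are and add age as a continuous covariate, with its form fixed in advance (log age, or a restricted cubic spline with stated knots). State that it carries through to 5.2.2, to the cost-effectiveness model in 5.3 and to the imputation model in 5.4. Add continuous SF ratio only if its numeric value at randomisation is recorded, and never derive it from post-randomisation readings. Settle this before outcome data are seen, in line with the purpose stated in section 1.1.

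The cost is one line of text and a few more model terms, any missing values being covered by the imputation already planned. The extra terms matter most in the mortality models. At the planning rate, 1836 × 0.075 is about 138 deaths by day 30, which leaves room for a few terms; log age uses only one. In the odds- and hazard-ratio models the conditional effect being estimated also changes slightly with the covariate set, so the report should name the covariates beside each adjusted estimate.

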5.2.3 Sensitivity analyses

Analysis of the primary clinical endpoint, and relevant secondary endpoints, will be repeated with duration of organ support measured in calendar days from randomisation to the last recorded day of organ support (capped at day 30). Duration of respiratory support will be reported using Kaplan-Meier methods with time measured from randomisation to the end of the last known period of respiratory support which started on or before day 30.

Unadjusted treatment effects for the two components of the composite primary clinical endpoint (days or organ support, and mortality by day 30) will be compared to confirmed that any treatment effect is in the same direction for both components. If this appears not to be the case, the partial proportional odds model⁶ will be used to estimate adjusted treatment effects.

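### SAP 5.2.1 would show the haemoglobin interaction for the ordinal primary outcome as an adjusted hazard ratio, which no model planned for that outcome produces

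*SAP*

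**What the plan says.** SAP section 5.1.1 defines the primary clinical outcome as a whole-number score: "surviving patients are scored by the number of calendar days on which any type of organ support was given", and patients who die by day 30 "are assigned the worst possible score of 31".

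Section 5.2.1 gives the analysis. The score is "compared between arms using a Wilcoxon rank-sum test with two-sided p-value of 0.05". The effect estimate is the probabilistic index, described in brackets as "the probability that the intervention is superior to the control for either mortality and/or duration of organ support". The regression model follows: "Ordered logistic regression will be used firstly in a sensitivity analysis to estimate the unadjusted proportional odds ratio", and then the same model adjusted for listed baseline variables. Section 5.2.3 adds that, if the two components of the composite appear to move in different directions, "the partial proportional odds model⁶ will be used to estimate adjusted treatment effects".

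Section 5.2.1 then lists three subgroup covariates: age in two groups, age-adjusted heart rate centile, and haemoglobin. It does not name the model in which the interactions are tested. For continuous covariates, with haemoglobin the only one named, the interaction "will be illustrated by calculating the adjusted hazard ratio within five categories at quintiles of the continuous variable".

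**The concern.** A hazard ratio comes from a time-to-event model, and the primary outcome is not analysed as a time to event. The display therefore cannot be produced from any model that the plan sets out for this outcome. The analyst would have to depart from the SAP or fit a model that was not pre-specified. Because the subgroup paragraph names no interaction model, the term hazard ratio is its only pointer to one, and it points away from the ordered logistic model described just above it. SAP section 1.1 says the plan is agreed before outcome data are inspected so that such choices are not driven by the data. This sentence leaves one open.

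A smaller matter in the same section is that the bracketed description of the probabilistic index does not say how equal scores count. Ties are certain with whole-day scores and a single score for all deaths.

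**Working it through.** **Hazard ratio.** No arithmetic applies. The check is which planned model could supply the measure.

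| Outcome | Planned method | Measure | SAP section |
|---|---|---|---|
| Primary score (0–30, death 31) | Wilcoxon rank-sum | Probabilistic index | 5.2.1 |
| Primary score | Ordered logistic, unadjusted and adjusted | Proportional odds ratio | 5.2.1 |
| Primary score, if components disagree | Partial proportional odds | Odds ratios | 5.2.3 |
| Mortality at 90 days and 12 months | Cox, if events allow | Hazard ratio | 5.2.2 |
| Time to liberation from ventilation | Cox: "Unadjusted and adjusted hazard ratios will be calculated using Cox regression" | Hazard ratio | 5.2.2 |

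No row for the primary score yields a hazard ratio. Section 5.2.3 also describes duration of respiratory support by Kaplan–Meier methods, but plans no hazard ratio for it. The adjusted measure available for the primary score is the proportional odds ratio.

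**Ties in the probabilistic index.** The plan states no figure here to reproduce.

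*Inputs from SAP section 2.3:* mean organ support 120 h against 108 h; 7.5% mortality in both arms; 2040 randomised with 10% loss, so 2040 × 0.9 = 1836 evaluable, or 918 per arm.

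*Assumptions, because the pilot data are not shown:* lognormal, gamma or exponential durations; randomisation at a uniformly distributed clock hour; hours converted to calendar days 1 to 30; deaths scored 31. The 12 h reduction is applied either as a multiplication by 0.9 or as a shift.

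*Formulas:*
- With identical arms, P(tie) = Σ pₖ², where pₖ is the probability of score k.
- Null value of P(better) alone = (1 − P(tie)) / 2.
- Quantity that the Wilcoxon test with mid-ranks addresses = P(better) + 0.5 × P(tie), with null value 0.5.

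*One case, lognormal with log-SD 0.6:*
- P(tie) = 0.108, so the literal null is (1 − 0.108)/2 = 0.446.
- Durations × 0.9: P(better) = 0.485 and P(tie) = 0.112. With half-ties, 0.485 + 0.5 × 0.112 = 0.541.
- Standard error at 918 per arm, ignoring the small tie correction: √(1/(6 × 918)) = 0.0135.

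*Range over the assumed shapes (exponential; gamma with CV 0.6–1.2; lognormal from log-SD 0.5 to CV 1.2):*

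| Quantity | Range |
|---|---|
| P(tie), no effect | 0.083 to 0.119 |
| Null of P(better) alone | 0.458 to 0.441 |
| P(better) alone under the planned benefit | 0.471 to 0.497 |
| P(better) + 0.5 × P(tie) under the planned benefit | 0.518 to 0.555 |

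**The case against.** The strongest reply is that hazard ratio is a slip for odds ratio. The adjusted proportional odds model is described a few lines earlier, and most analysts would use it. That is plausible, and it limits the weight of the point. The sentence is still wrong as it stands and should be corrected before it is followed.

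Four stronger readings are tempting, and the document does not support them.

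- A reader might infer that all the subgroup results are affected. The sentence covers continuous covariates only and names haemoglobin. Age is binary and heart rate is grouped into centile bands. The hazard ratio also only illustrates the interaction and does not test it.
- A reader might infer that the SAP has no model giving hazard ratios. It has Cox models, but for secondary outcomes. The statement holds for the primary outcome alone.
- A reader might infer that the direction of benefit would be reversed. That presupposes a Cox model for time to end of organ support, which the SAP never plans.
- A reader might infer that the probabilistic index is wrong and would make a benefit look like harm. The bracketed words are a plain-language gloss on a named index, paired with a Wilcoxon test that implies half-ties. They give no formula, do not say that ties are discarded and state no null value. Even taken literally, 0.485 lies (0.500 − 0.485)/0.0135 ≈ 1.1 standard errors below 0.5, and under a 12 h shift most shapes give about 0.497. Against 0.5 that would look like little or no difference.

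**Conclusion.** The hazard-ratio wording in SAP section 5.2.1 is an error. It assigns to the ordinal primary outcome an effect measure that none of that outcome's planned models produces. This follows from the text alone. Its reach is narrow: one illustrative display, for haemoglobin. That ordered logistic regression is the intended interaction model is an inference, since the section does not name one, but it is the only adjusted model that 5.2.1 gives for this outcome.

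The tie point is a clarification. The document does not show that a wrong statistic would be calculated. Its size, a literal null of about 0.44 to 0.46 where the Wilcoxon-matched index has 0.5, rests on assumed duration shapes and the resulting 8% to 12% of tied pairs.

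Neither point affects the primary test, the two-sided 0.05 level or the sample size of 2040.

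**What to change.** In section 5.2.1, replace the adjusted hazard ratio with the adjusted proportional odds ratio from the ordered logistic model that includes the treatment-by-covariate interaction. This also names the interaction model, which the section now leaves unstated.

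As a minor addition in the same section, define the probabilistic index as P(intervention score better) + 0.5 × P(scores equal), with null value 0.5, so that it matches the Wilcoxon test reported with it.

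The cost is two sentences in the SAP. No data collection, test or sample size changes.
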